
General Exclusion Criteria
	
 1. Inability to undergo CT angiography and/or CT perfusion imaging (e.g., renal insufficiency, iodine/contrast allergy) 2. Co-morbid psychiatric or medical illnesses that would confound the neurological assessments 3. Treatment with IV thrombolytic therapy beyond 4.5 hours from last known well 4. Treated with IV thrombolytic therapy 3-4.5 hours 3-4.5 hours after last known well AND any of the following: 
 1) age >80, 2) current anticoagulant use, 3) history of diabetes AND prior stroke, 4) NIHSS >25, 5) ischemic involvement of > 1/3 MCA territory 5. Current participation in another investigational drug or device study.

Imaging Inclusion Criteria
	
 1. Proven large vessel occlusion in ICA or MCA-M1 occlusion (carotid occlusions can be cervical or intracranial, with or without tandem MCA lesions) determined by MRA or CTA 2. Large infarct-core lesion on at least one of the following 
 2.1. Non-Contrast CT (ASPECTS of 3-5), 2.2. CT perfusion (rCBF<30% ≥50cc), 2.3. MRI-DWI (ADC<620 ≥50cc)

Imaging Exclusion Criteria
	
 1. Patients who have both ASPECTS of 6-10 on non-contrast CT AND core volume <50 cc on perfusion imaging 2. Patients with very large core on non-contrast CT i.e. ASPECTS ≤ 2 3. Evidence of intracranial tumor (except small meningioma), acute intracranial hemorrhage, neoplasm, or arteriovenous malformation 4. A significant mass effect with midline shift 5. Evidence of internal carotid artery dissection that is flow limiting or aortic dissection 6. Intracranial stent implanted in the same vascular territory that precludes the safe deployment/removal of the neurothrombectomy device 7. Acute symptomatic arterial occlusions in more than one vascular territory confirmed on CTA/MRA (e.g., bilateral MCA occlusions, or an MCA and a basilar artery occlusion). 8. Signs of established infarct and large area of cerebral edema on non-contrast CT

Primary Outcome
	
 1. Modified Rankin Scale (mRS) at 90 (+/- 15) days. The primary outcome is a shift on 90-day mRS. 2nd primary outcome is favorable clinical outcomes: mRS score of 0-2.

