Limited non-randomized evidence of thrombectomy efficacy is available in the published literature. A recently published study, a meta-analysis of 7 early window randomized controlled trials by Campbell et al.¹⁴ has suggested benefit of thrombectomy in patients presenting with infarct core of >100 cc. Campbell et al. demonstrated that although functional independence rates remain very low, these patients continue to benefit from thrombectomy. For infarct core volumes up to 125 cc, the number needed to treat for any benefit remains below 10 for most functional outcomes and less than 5 for any functional improvement. In the light of these recently available evidence, these patients may have a low likelihood of functional independence but could still have better functional outcome than patients treated with medical management only. Thus, the protocol was amended to include these patients in the study. Stringent safety monitoring of mortality and symptomatic ICH is employed to ensure patient safety. The amended inclusion criteria will allow for:

- 1) Assessment of population with CTP/MRP core infarct >100cc
- 2) More generalizability of the study findings
- 3) No dependency on perfusion criteria, which will allow for the population to be treated based on non-contrast CT only. Providing data on the efficacy and safety of thrombectomy selection based on a non contrast CT, which is more readily available, would result in an increased thrombectomy availability to centers without perfusion imaging.

Although no upper limit is specified for infarct core volume measurements on CT or MR perfusion imaging, the infarct size is still expected to be limited, to an extent, given imaging exclusion criteria of “Patients with very large core on non-contrast CT i.e. ASPECTS ≤ 2 ” and

patients with “signs of established infarct and large area of cerebral edema on non-contrast CT”.

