3.2. Enrollment Inclusion and Exclusion Criteria

Adult patients with AIS due to LVO in the anterior circulation (ICA and MCA occlusions in the M1 segment) who are normal or with minimal deficits at the time of their strokes (mRS 0-1), have received the pre-specified imaging profile (NCCT, CTA and CTP/MRP) prior to the treatment decision, and will be treated with thrombectomy (groin puncture time) plus medical management or medical management alone within 24 hrs from their last-known-well are eligible for the study (Table 1). A screening log of all patients with LVO presenting within 24 hours of symptom onset who receive thrombectomy, in addition to non-enrolled patients who qualify for SELECT 2 large core definition on imaging, will be kept. Clinical data will be collected to evaluate which method best correlates with patient outcome after thrombectomy. Mechanical thrombectomy includes the use of stent retrievers (e.g. Trevo[®], Solitaire[®], EmboTrap Revascularization Devices) and/or aspiration devices (e.g. MicroVention SOFIA Catheter, and Penumbra) as recommended by AHA (American Heart Association) guidelines. Please review Appendix C for a list of all approved devices.

Table 1. The SELECT 2 study inclusion and exclusion criteria

Inclusion Criteria	
 1) Adults (18-85 years) with the final diagnosis of an acute ischemic stroke 2) NIHSS \geq 6 3) Last known well to groin puncture or medical management between 0 to 24 hours 4) Pre-stroke modified Rankin Scale score of 0-1 5) Eligible for thrombectomy or medical management 6) Signed Informed Consent obtained 7) Subject willing to comply with the protocol follow-up requirements 8) Anticipated life expectancy of at least 3 months
---------------------------	---

Exclusion Criteria	
1) Inability to undergo CT-Angiography and/or CT/MR Perfusion imaging (e.g., renal insufficiency, iodine/contrast allergy)2) Co-morbid psychiatric or medical illnesses that would confound the neurological assessments3) Treatment with IV thrombolytic therapy beyond 4.5 hours from last known well4) Treated with IV thrombolytic therapy 3-4.5 hours after last known well AND any of the following:
- age >80- current anticoagulant use- history of both diabetes AND prior stroke- NIHSS >25- ischemic involvement of more than third of the MCA territory5) Current participation in another investigational drug or device study.

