After obtaining consent and ensuring all inclusion and exclusion criteria are met, randomization will be done in the emergency room prior to treatment using a web-based dynamic randomization system. Our randomization algorithm will be accessible to the study investigators and staff through a separate web page accessible only through the REDCAP database module. Covariate adaptive randomization will be used to balance the distribution of age (<60, 60-69, 70-79, 80-85 years old), presentation NIHSS (6-9, 10-15, 16-20, >20), center, clot location (M1, ICA), treatment time window (0-8, 9-16, 17-24 hours from onset to randomization time), CTP/MRP core volume (<50cc, 50-100cc, >100cc), presence or absence of target mismatch profile (mismatch ratio ≥ 1.8 & mismatch volume ≥ 15 cc) and hemisphere (right, left) between the two treatment groups.

The randomization algorithm we are going to implement is the algorithm developed by Pocock and Simon (1975)²⁷, i.e., minimization method. Through this algorithm, the assignment of a new patient to a treatment group is determined so as to minimize the differences between the groups in terms of these important key baseline variables. Unlike traditional stratified randomization, the minimization method works toward minimizing the total imbalance for all factors together instead of considering mutually exclusive subgroups, that is, we will not be creating these mutually exclusive subgroups during the randomization. Therefore, this approach is not restricted by the number of variables and the possible combinations of levels of balancing factors. Further details about Randomization can be found in Appendix A.

Eligible patients will be randomized into thrombectomy plus medical management vs medical management alone at a 1:1 ratio. The minimization algorithm is intended to balance the baseline characteristics between the two study arms, thrombectomy vs. medical management. The algorithm is not intended at the level of imaging profile subgroup. When a new patient is enrolled, the site will enter the stratification factor values into the dynamic randomization webpage and the treatment assignment will be determined immediately. An emergency 1-800 number will be provided if web-based randomization is not available due to exigent circumstances.

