6.1. Sample Size justification, Adaptive Enrichment Design, and Statistical Analysis Plan

The study will implement a novel adaptive enrichment design that will not only allow the trial to stop early for efficacy but also allow to select and evaluate the treatment effect in a most promising subpopulation if futility rule is triggered at the interim (or final) analyses in the overall population. This adaptive design has been developed, well-studied, and implemented for the DEFUSE 3 studies²⁴. The details and theory of this adaptive enrichment design are summarized in Lai et al (2014)²⁵ and Lai et al (2018)²⁶. This adaptive enrichment design is an extension of standard group sequential design with an enrichment feature²⁵. It will test for efficacy or futility with two interim analyses and a final analysis. This adaptive design was chosen because the preliminary data from the SELECT study suggest a potential heterogeneity in thrombectomy treatment effect based on the different imaging profiles. By adopting this adaptive design, we expect to reallocate future accrual and study treatment effects only in a most promising subpopulation when there is evidence to show that EVT is futile in the overall population at interim (or final) analyses. By limiting the subsequent enrollment only in the most promising subpopulation, a larger number of patients will eventually be enrolled in this subgroup for efficacy testing compared to traditional designs.

This design uses the Generalized Likelihood Ratio (GLR) statistic (Kullback-Leibler criterion) as criteria to identify the subgroup, which has the best chance of showing a benefit from EVT.

Through these criteria, it can achieve optimal balance simultaneously between the estimated size of the treatment effect and the sample size of the subgroup. By considering the CTP core volume and treatment time window, the patients are split into six disjoint groups, that is Group 1 (ASPECTS 3-5 and CTP/MRP core volume <50cc) at early time window 0-12 hours (denoted as **G1A**), Group 1 at late time window 12-24 hours (denoted as **G1B**), Group 2 (ASPECTS 6-10 and CTP/MRP core volume \geq 50cc) at early time window (denoted as **G2A**), Group 2 at late time window (denoted as **G2B**), Group 3 (ASPECTS 3-5 and CTP/MRP core volume \geq 50cc) at early time window (denoted as **G3A**), and Group 3 at late time window (denoted as **G3B**).

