Secondary analyses: Our secondary endpoint is the proportion of patients with mRS 0-2 at day 90 (indicating functional independence). The difference in the proportions of patients with mRS 0-2 between treatment arms will be assessed using logistic regression. We will adjust for the variables we used in adaptive randomization program in the logistic regression model. Other secondary endpoints include (1) the safety outcomes measured by the incidence of sICH, neurological worsening, mortality, groin hematomas, infections or vascular injury, (2) infarct volume, lesion growth, successful reperfusion, and recanalization rate, (3) length of hospital stay, and (4) discharge disposition. The exploratory analyses on secondary outcomes will include descriptive statistics (mean [\pm standard deviation, SD] or median and interquartile range for continuous variables and frequency [percentage] for discrete variables) and appropriate test for secondary outcome variables between two groups. For binary outcomes (e.g., sICH, neurological worsening, mortality, groin hematomas, infections or vascular injury, successful reperfusion, recanalization), Chi-square or Fisher's exact test where appropriate will be used to compare the incidence between two treatment groups for large core patients. We will also apply the logistic regression model on these outcomes after adjusting for the variables we used in adaptive randomization program. The adjusted odds ratio (OR), as well as 95% confidence interval will be reported. For the length of stay, mean \pm SD and median (Interquartile range) will be calculated for each group. For continuous variables (e.g., the length of stay and infarct volume), two sample t-test or Wilcoxon rank sum test as appropriate will be applied to compare them between two groups. For discharge disposition, frequency and percentage of each disposition will be reported and Chi-square test or Fisher's exact test where appropriate will be applied to compare its distribution between two groups.

Subgroup analyses: Subgroup analyses of the effect of thrombectomy on the primary and secondary endpoints will be performed. Subgroups will be defined based on the stratification variables, key demographic factors (such as race and ethnicity), thrombolysis vs. no thrombolysis, CTP vs. MRI selection, and witnessed vs. unwitnessed symptom onset, wake-up vs non-wake-up stroke, and TIC1 0-2a vs. TIC1 2b/3 results in the cath lab. An additional

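### The protocol cites evidence for CT-only selection as a reason for its criteria, but plans no thrombectomy estimate in ASPECTS 3-5 patients and omits ASPECTS from the adjusted models and subgroup list

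*Combined protocol and SAP*

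**What the plan says.** - **Goal.** Section 1.3 lists three things that the amended criteria allow. The third is freedom from perfusion criteria: "Providing data on the efficacy and safety of thrombectomy selection based on a non contrast CT", for the benefit of centers without perfusion imaging.
- **Eligibility.** "Non-Contrast CT (ASPECTS of 3-5" qualifies a patient alone. The imaging exclusions remove "Patients who have both ASPECTS of 6-10 on non-contrast CT AND core volume <50 cc on perfusion imaging". Section 3.2 requires that patients "have received the pre-specified imaging profile (NCCT, CTA and CTP/MRP) prior to the treatment decision", so both readings should exist for everyone randomized.
- **Groups.** Section 6.1 defines all three imaging groups by ASPECTS and core volume together, for example "Group 1 (ASPECTS 3-5 and CTP/MRP core volume <50cc) at early time window 0-12 hours". Group 2 is ASPECTS 6-10 with core of at least 50 cc. Group 3 is ASPECTS 3-5 with core of at least 50 cc.
- **Minimization.** The factors are age, NIHSS, center, clot location, time window, core volume, target mismatch and hemisphere. ASPECTS is not one of them, and the randomization text says openly: "The algorithm is not intended at the level of imaging profile subgroup".
- **Adjusted analyses.** The stratified CMH analysis and the logistic models in Section 6.1 use the minimization variables, so they omit ASPECTS.
- **Subgroups.** "Subgroups will be defined based on the stratification variables, key demographic factors (such as race and ethnicity", followed by further named factors. ASPECTS is not named.
- **Analyses that use ASPECTS-defined groups.** Section 6.2 compares the two discordant profiles (Groups 1 and 2) and tests their interaction with treatment. Analysis 3 (Sections 3.1 and 19) tests EVT against MM in favorable CT with unfavorable perfusion, which is Group 2.

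**The concern.** A center without perfusion imaging can recognize a large core only by ASPECTS 3-5. Its question is whether thrombectomy helps those patients as a whole, which means Groups 1 and 3 combined. The trial will enroll them in large numbers and record ASPECTS on each, yet plans no estimate of the effect in them. Analysis 3 serves the favorable-CT side of CT-based selection, following the argument of Section 1.6, but has no counterpart for ASPECTS 3-5.

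If the estimate is first defined after unblinding, it will be read as post hoc. If enrichment occurs, the choice of which ASPECTS 3-5 patients to count will also be made with the results in view.

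**Working it through.** **1. The plan's own figure.** From the projected mRS table in Section 6.1, the probability that an EVT patient does better than an MM patient, ties counted half, is 0.59375. The tie-corrected rank-scale effect is 0.335. The total is N = 4 × ((1.960 + 1.282)/0.335)² ≈ 375, which agrees with the stated 376. The scale used below is therefore the plan's own.

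**2. Size of the CT-selected population.** The Section 6.1 mix is G1A 14%, G1B 6%, G2A 14%, G2B 6%, G3A 42%, G3B 18%.
- ASPECTS 3-5 = 14 + 6 + 42 + 18 = 80%, so 448 of 560. Group 3 is 60/80 = 75% of them.
- Section 6.2 compares Groups 1 and 2 only, so it leaves out that 75%.

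**3. What eligibility already covers.** ASPECTS 6-10 with core below 50 cc is excluded, so core below 50 cc identifies Group 1. Core volume is a minimization factor and hence a subgroup variable. Its 50-100 cc and >100 cc levels mix Groups 2 and 3. That contrast is the uncovered part.

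**4. The overall effect is not a substitute.** The effect in ASPECTS 3-5 is (0.2 × Group 1 effect + 0.6 × Group 3 effect)/0.8. In Table 3:
- Scenario #3: (0.2 × 0.4 + 0.6 × 0)/0.8 = 0.10, against 0.16 overall.
- Scenario #4: (0.2 × 0.4 − 0.6 × 0.1)/0.8 = 0.025, against 0.10 overall.

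**5. Precision of the missing estimate.** Half-width = 1.96 × 2/√n, with 1:1 allocation, unit SD and no missing data.

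| Total randomized | ASPECTS 3-5 | Half-width |
|---|---|---|
| 560 | 448 | 0.19 |
| 376 (Table 3 average, scenario #1) | 301 | 0.23 |
| 380 (second interim) | 304 | 0.22 |
| 200 (first interim) | 160 | 0.31 |

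**6. If enrichment occurs.** None of the five candidates is Groups 1 + 3. Suppose Group 3 closes and accrual continues to 560.
- First interim: Group 3 stays at 120. Group 1 reaches 40 + 360 = 400 if Group 1 is selected, or 40 + 180 = 220 if Groups 1 + 2 are. Group 3's share of ASPECTS 3-5 falls from 75% to 120/520 = 23% or 120/340 = 35%.
- Second interim: Group 3 stays at 228, and Group 1 reaches 256 or 166. The share falls to 47% or 58%.

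Simple pooling would then no longer describe a CT-selected population. Reweighting to 25:75 gives SE = 2 × √(0.25²/n₁ + 0.75²/n₃). At the first interim this is 0.139 to 0.141 (half-width 0.27 to 0.28). At the second it is 0.104 to 0.107 (0.20 to 0.21).

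**7. Value of ASPECTS as a covariate.** Figure 3 gives good-outcome rates of 32% (Group 2 profile) and 20% (Group 3 profile). At 25:75 the mean rate is 0.23, and the share of variance explained is 0.25 × 0.75 × 0.12²/(0.23 × 0.77) = 1.5%.

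**The case against.** Several counter-arguments have force.

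- **The goal is rationale, not an aim or endpoint.** True. This limits the weight of the point, but a stated reason for widening entry still deserves a named analysis.
- **The primary comparison is about 80% ASPECTS 3-5.** A positive overall result does bear on the goal. Step 4 shows that it can differ from the effect in ASPECTS 3-5 under the plan's own scenarios.
- **ASPECTS is used in the second aim and Analysis 3, and core volume captures Group 1.** Both are correct, and they narrow the gap to Group 2 versus Group 3 plus the missing combined estimate.
- **The 0.19 half-width is a best case.** Agreed: the trial may stop early, hence the 0.23.
- **The 32% versus 20% is weak evidence.** It comes from a non-randomized cohort, without counts, so 1.5% is only indicative.

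Stronger readings are tempting, and the documents do not support them.

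- **Enrichment destroys the CT-only evidence.** It weakens it. About 160 ASPECTS 3-5 patients are in by the first interim and 304 by the second. Nor does all of Group 3 necessarily close: candidate G1A+G1B+G2A+G2B+G3A drops only G3B and keeps every early-window ASPECTS 3-5 patient. It remains true that under every candidate a late-window claim needs perfusion to define its patients.
- **Leaving ASPECTS out of minimization biases the test or leaves the enrichment cells unbalanced.** Omission does not bias the comparison, and the plan discloses the choice. Simulations of Appendix A at 200 patients (30 centers, invented distributions for the other factors, mismatch weight 1 or 2) gave an arm difference of 8 or more in G1A in about 1% of runs, and in Group 2 in about 16 to 18%, against about 24% in Group 2 for a plain coin toss. This gives no ground for changing the minimization factors or time cuts.

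**Conclusion.** The point holds as a gap in the analysis plan, not as an error in the primary test. About 80% of expected patients make up the population that CT alone would select. The effect in them could be estimated to within about 0.19 to 0.23 standardized units against a projected 0.34, and no section plans to do so. The covariate omission matters less, at about 1-2% of outcome variance.

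The figures rest on the Section 6.1 group mix, unit SD and complete follow-up. How often enrichment would intervene can only be gauged. A rough simulation with the stated bounds put enrichment at an interim at about 2% in scenario #1, 26% in #3, 46% in #4 and 80% under the null. It did not match Table 3 closely (scenario #1 power 88.8% against 86.0%, average size 362 against 376), and the relaxed subgroup futility bound in it was assumed.

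**What to change.** 1. Add ASPECTS as a covariate in the adjusted mRS analysis and the logistic models of Section 6.1.
2. Add ASPECTS 3-5 versus 6-10 to the subgroup list, with a treatment interaction test. Name the EVT effect on the ordinal mRS in ASPECTS 3-5, with a 95% CI and no alpha claimed, as the analysis for the Section 1.3 goal.
3. State now what happens under enrichment. Either use only patients randomized before it, or reweight Groups 1 and 3 to their original mix (by time window as well if the selected candidate splits a group by window). Report that the estimate is weakened and, because it follows a futility trigger, that pre-enrichment data will tend to understate the effect.

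The cost is SAP wording, one covariate already read before randomization, and one more non-confirmatory subgroup estimate. The primary test, its bounds and the randomization program do not change.

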1.4. Rationale for excluding patients with very large core on CT (ASPECTS 0-2)

There are no previously published data to describe the outcomes in this patient population. We did not have any patients with ASPECTS 0-2 who received a thrombectomy in SELECT trial. The 90-day mRS distribution for patients with ASPECTS 0-2 is shown in Figure 2. Since, no data for thrombectomy efficacy and safety is available, these patients were excluded from the trial.

[figure not shown]

Figure 2. Modified Rankin Scale (mRS) distribution bars representing 90day clinical outcomes in large core patients stratified by ASPECTS score.

1.5. Imaging selection for thrombectomy

Thrombectomy is a highly effective treatment for anterior circulation LVO patients based on the results of several recent randomized clinical trials¹⁻⁷. However, the imaging modalities and the patient populations enrolled, varied between the studies. For example, the Multicenter Randomized Clinical Trial of Endovascular Treatment for Acute Ischemic Stroke in the Netherlands (MR CLEAN)¹ used non-contrast head CT (NCCT) with the inclusion criteria of less than one third of the MCA, while the Solitaire with the Intention for Thrombectomy as Primary Endovascular Treatment trial (SWIFT PRIME)⁴ and the Randomized Trial of Revascularization with Solitaire FR Device versus Best Medical Therapy in the Treatment of Acute Stroke Due to Anterior Circulation Large Vessel Occlusion Presenting within Eight Hours of Symptom Onset (REVASCAT)³, in spite of using NCCT, applied a more stringent inclusion criterion of the Alberta Stroke Program Early CT Score (ASPECTS) of ≥ 6 . Some of the patients in SWIFT PRIME⁴ were treated by CT-Perfusion/ iSchemaView RAPID (CTP/RAPID), while some in REVASCAT³ were treated based on MRI ASPECTS (≥ 7). Thrombectomy for Small Core and Anterior Circulation Proximal Occlusion with Emphasis on Minimizing CT to Recanalization Times (ESCAPE)² used more specific imaging criteria focusing on NCCT ASPECTS (≥ 6) and CT-Angiography collaterals, as well as placing some consideration of the CT-Perfusion profile. Extending the Time for Thrombolysis in Emergency Neurological Deficits — Intra-Arterial trial (EXTEND-IA)⁵ was the sole early window trial that purely based imaging selection on advanced perfusion imaging using CTP/RAPID.

This resulted in uncertainty in regards to optimal patient selection when it comes to imaging modality prior to thrombectomy as reflected in the current AHA guidelines, and the guideline recommending against using advanced perfusion imaging for patients presenting in early time window was recently rescinded⁸.

The recent trials evaluating thrombectomy effectiveness in the late time window - Clinical Mismatch in the Triage of Wake Up and Late Presenting Strokes Undergoing Neurointervention With TREVO (DAWN)⁶ and Endovascular Therapy Following Imaging Evaluation For Ischemic Stroke 3 (DEFUSE3)⁷ used advanced imaging perfusion (CTP and MR-Perfusion) utilizing the RAPID software along with NCCT criteria to select patients. As a result, the recent AHA guidelines also recommend the use of both CT and advanced perfusion imaging for patient selection in thrombectomy⁸.

In conclusion, the optimal imaging selection modality prior to thrombectomy is still unknown. Furthermore, the restrictive imaging inclusion criteria and correlation with outcomes, both functional independence, and safety outcomes are still yet undetermined. To measure the correlation between the two different imaging modalities and clinical outcomes, patients with discordant imaging profiles should be compared.

The highest level of evidence comes from a randomized controlled trial comparing thrombectomy outcome rates as well as safety parameters in patients selected by CT only vs CT plus perfusion imaging. However, a randomized trial is not feasible given the level of evidence from RCTs in the late window patients treated based on favorable perfusion imaging profiles (DAWN⁶ and DEFUSE 3⁷). Additionally, the current AHA guidelines recommend the use of perfusion imaging for selection of patients in the late window⁸.

Since the clinical trials evaluating thrombectomy largely included patients with favorable profiles on both CT and perfusion imaging, the vast majority of the currently available data is on these patients. Thus, the correlation between the thrombectomy outcome rates with different imaging profiles, specifically with discordance profiles between CT and perfusion images, is not well established. However, those patients with discordant imaging profiles on both modalities are frequently encountered in real-world practice. There is currently no evidence from randomized trials to guide the treatment decision in these patients. Many of these patients

may be excluded from the treatment based on the unfavorable profile on one imaging modality as preferred by the treating center or physician. Moreover, it is unclear if a favorable profile on advanced perfusion imaging with an unfavorable profile on non-contrast CT will provide improved prognostic value of thrombectomy when compared to patients with unfavorable perfusion imaging and favorable CT, or vice versa.

The SELECT trial was the first and only study to document discordance between imaging selection profiles. In SELECT, we observed that the two imaging modalities (CT and CT perfusion) had an agreement with favorable profiles in 81% of patients and an unfavorable profile on both modalities in 4% of patients. Discordance between the two imaging modalities was observed in 15% of patients with 7% showing favorable CT but unfavorable CTP and 8% showing unfavorable CT but favorable CTP. The agreement between imaging modalities and outcomes are shown in Figure 3.

Good CT profile Good CTP profile
 
81% Good 90day mRS= 59%
 
A
	
Poor CT profile Good CTP profile
 
8% Good 90day mRS= 48%
 
B

Good CT profile Poor CTP profile
 
7% Good 90day mRS= 32%
 
C
	
Poor CT profile Poor CTP profile
 
4% Good 90day mRS= 20%
 
D

Figure 3. Illustration of patients’ imaging profiles, as determined by the core lab, and their outcomes. A (Favorable CT & Favorable CTP): High agreement between **CT and CTP profiles** prior to thrombectomy. Similar profile to patients enrolled in prior RCTs; B (Unfavorable CT & Favorable CTP): Patients who would have been excluded by CT but treated based on favorable CTP; C (Favorable CT & Unfavorable CTP): Patients who would have been excluded by CTP but qualified by favorable CT; D (Unfavorable CT & Unfavorable CTP).

As shown above, discordance between imaging profiles was not uncommon and clinical outcomes differed based on the presence and type of discordant imaging profiles. Patients with discordant profiles showed outcomes better than patients with both imaging modalities demonstrating an unfavorable profile.

The two groups where both imaging modalities (CT and perfusion imaging) agree:

1. Unfavorable profiles on both: the results would not contribute to the comparison of imaging selection.
2. Favorable profile on both: there is, as detailed, strong evidence from RCTs supporting thrombectomy in both early and late time windows; thus randomizing these patients to compare imaging selection for thrombectomy is unethical and not feasible.

In SELECT 2, in order to compare the outcomes between imaging selection modalities, we propose to examine the correlation between the discordance in imaging profile and outcome rates, both functional independence as well as safety outcomes. We also propose to examine if there is a heterogeneity of treatment effect of thrombectomy in patients with discordant imaging profile (favorable CT/unfavorable perfusion imaging and unfavorable CT/favorable perfusion imaging).

Based on the SELECT trial results, patients with unfavorable CT/ favorable CTP had 48% good outcomes vs favorable CT/unfavorable CTP with 32% good outcomes (16% absolute difference). A superiority margin at 15% will be set between the two discordance groups and good outcome rates between patients with discordant imaging profiles will be compared. If those differences do not reach the statistical margin, then among patients with discordant imaging profile who met the inclusion criteria for SELECT 2 and treated with thrombectomy, the outcome rates did not differ.

In addition to comparing the rates of good outcomes between patients treated with thrombectomy in patients with discordant profiles, thrombectomy treatment effect heterogeneity will be assessed in patients with favorable CT/ unfavorable perfusion imaging and those with unfavorable CT/favorable perfusion imaging. If no heterogeneity exists, then thrombectomy benefit is not modified in the two scenarios when the two imaging modalities disagree.

1.6. Thrombectomy efficacy and safety in patients with favorable CT but unfavorable perfusion imaging profile

Early window trials demonstrated the superiority of thrombectomy over standard medical management in patients selected by either favorable CT (ESCAPE and REVASCAT) or favorable perfusion imaging (EXTEND-IA and a portion of SWIFT-PRIME). Thus, in patients with favorable CT profile, thrombectomy is proven superior to standard medical management in early window. Late window trials, DAWN⁶ and DEFUSE 3⁷ proved thrombectomy efficacy and safety in patients with favorable CT and perfusion imaging profiles. If thrombectomy is proven better than medical management only in patients with favorable CT but unfavorable perfusion imaging, then regardless of the perfusion imaging findings, patients with favorable CT would benefit from thrombectomy and thus, should be treated with thrombectomy.

